10. ASSESSMENT OF EFFICACY

10.1 Study Endpoints

Primary Endpoint

- Change and percent change in the individual BBSS scores of the three patient reported outcomes (dysmenorrhea, dyspareunia and non-menstrual pelvic pain) by study visit and treatment cycle.

Secondary Endpoints

- Change in daily average use and percent change of prescription medications from the baseline menstrual cycle to the matching period leading up to Week 18, the last day of dosing of the first cycle of treatment.
- Change in daily average use and percent change of over the counter medications from the baseline menstrual cycle to the matching period leading up to Week 18, the last day of dosing of the first cycle of treatment, calculated based on days with reported values.
- Change in daily average use and percent change of overall medication use, prescription and over the counter, from the baseline menstrual cycle to the matching period leading up to Week 18, the last day of dosing of the first cycle of treatment, calculated based on days with reported values.
- Change and percent change in BBSS score incorporating the two physician-reported scores by study visit and treatment cycle.
- Change from baseline in endometrial pain assessed using a Visual Analog Scale (VAS) by study visit and treatment cycle.
- Change from baseline in daily average dysmenorrhea and non-menstrual pelvic pain using an 11-point numerical rating scale (NRS) by study visit and treatment cycle.

11.1 Adverse Events

11.1.1 Reporting Adverse Experiences

Any AE (clinical sign, symptom, or disease) temporally associated with the use of this investigational drug, whether or not considered related to the investigational product, shall be documented on the CRF. All AEs reported by the subject or observed by the Principal Investigator will be individually listed. The signs and symptoms, time of onset (24-hour clock), duration, action taken and follow-up procedures will be reported.

11.1.2 Definitions

Adverse Event – Any untoward medical occurrence in a clinical investigation subject administered a drug and does not necessarily have a causal relationship with this treatment. An AE can therefore, be any unfavorable and unintended sign (including an abnormal laboratory finding), symptom, or disease temporally associated with the use of an investigational product, whether or not related to the investigational product.

Serious Adverse Event (SAE) – An adverse drug experience that results in any of the following outcomes: death, a life-threatening experience, requires or prolongs subject hospitalization, results in persistent or significant disability/incapacity, or is a congenital anomaly or birth defect.

Cases of liver transaminases that increase above 3 times the upper limit of normal must be reported as SAEs regardless of whether the above defined SAE criteria are met.

Unexpected Adverse Event: Any adverse event that is not identified in nature, severity, or frequency in the current Investigator's Brochure.

Additionally, the Principal Investigator will evaluate all AEs as follows:

Action taken: whether or not the AE caused the subject/patient to discontinue the study medication.

Intensity, to be graded as:

DEGREE	DESCRIPTION
Mild	Awareness of signs and symptoms; easily tolerated
Moderate	Discomfort sufficient to interfere, but not prevent daily activity
Severe	Unable to carry out usual activity

Relationship to study medication, to be graded as:

DEGREE	DESCRIPTION
Definitely	There is evidence of exposure to the study drug, for example, reliable history or acceptable compliance assessment; the temporal sequence of the AE onset relative to the medication is reasonable; the AE is most likely to be explained by the treatment than by another cause; the AE shows a pattern consistent with previous knowledge of the treatment.
Probably	There is evidence of exposure to the study drug; the temporal sequence of the AE onset relative to medication administration is reasonable; the AE is more likely explained by the treatment than by another cause.
Possibly	There is evidence of exposure to the study drug; the temporal sequence of the AE relative to the medication administration is reasonable; the AE could have been due to another equally likely cause.
Probably not	There is evidence of exposure to the study drug; there is another more likely cause of the AE.
Definitely not	The subject/patient did not receive the study drug; or temporal sequence of the AE onset relative to administration of the study drug is not reasonable; or there is another obvious cause of the AE.

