8.3 Selection and Withdrawal of Subjects

Subjects for the study will be selected during screening based on the inclusion and exclusion criteria and clinical assessments listed below. Subjects will be discontinued from the study prematurely if:

- Unacceptable adverse events occur considered by the investigator to be associated with use of the study drug
- The subject requests to be withdrawn from the study
- Any of the following occur:
 - ALT or AST >8xULN

- ALT or AST $>5\times$ ULN for more than 2 weeks
- ALT or AST $>3\times$ ULN **and** (TBL $>2\times$ ULN **or** INR >1.5)
- ALT or AST $>3\times$ ULN with the appearance of fatigue, nausea, vomiting, right upper quadrant pain or tenderness, fever, rash and/or eosinophilia ($>5\%$)
- A need arises for concomitant medication prohibited by the protocol
- The Principal Investigator decides that it is in the subject's best interest
- The subject is noncompliant with the protocol
- Any subject who develops an endometrial thickness ≥ 18 mm will undergo endometrial biopsy. The endometrial biopsy will be forwarded to a member of the Expert Panel for expedited review. If the biopsy shows EIN or hyperplasia (per Expert Panel review), subject will be discontinued from the study. If EIN or hyperplasia is diagnosed the sponsor will be notified and subject discontinued from the study. Appropriate follow up treatment will be provided as deemed necessary by the investigator.
- Any subject who experiences heavy bleeding (bleeding intensity of 4 or more per the Daily Diary Card in [Appendix 3](#)) for 7 consecutive days or more will be discontinued from the study. This does not apply if heavy bleeding occurs in the first recovery menses after withdrawal of drug at the end of treatment, or is no heavier than bleeding was prior to treatment.
- Any subject who develops an endometrial thickness ≥ 18 mm and excessive bleeding that requires dilatation and curettage or hysterectomy will be discontinued from the study and undergo endometrial biopsy. Women with such findings will not be eligible for extension of treatment. Appropriate follow up treatment will be provided as deemed necessary by the investigator.
- Subjects with a biopsy that shows clear evidence of neoplasia, as determined by the expert panel, will be discontinued and be ineligible for extension of treatment.

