11.1.3 Serious Adverse Events (SAEs)

The Principal Investigator shall document all SAEs in all subjects after signing informed consent [REDACTED] and they must be reported to the Repros Therapeutics Inc. Safety Monitor within 24 hours by Fax or telephone, even if the SAE does not appear to be drug-related. This report should include all available information at the time of notification. This notification should be followed with submitting a SAE Report Form provided by Repros Therapeutics Inc. All additional follow-up reports must be reported to the Repros Therapeutic Inc. monitor as soon as available.

Cases of liver transaminases that increase above 3 times the upper limit of normal must be reported as SAEs regardless of whether the above defined SAE criteria are met.

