6.8.1 Adverse Events (AEs)

Treatment-emergent AEs (TEAEs) are defined as those AEs with an onset date and time equal to or after the start of study medication in stage 2, or those events in which the onset date and time are before the start of study medication but worsened after the start of study medication. To be conservative, in the case of a missing onset time for an AE, an AE with a start date equal to or after the dosing date will be considered treatment-emergent. AE's with missing onset dates will also be considered treatment-emergent.

All TEAEs will be summarized by treatment group. The number of TEAEs as well as the number and percentage of subjects who experienced at least one TEAE will be summarized for each system organ class and each preferred term. The percentage will be based on the number of subjects included in the Safety population. Each subject will contribute at most one count per summarization category.

If a subject has more than one AE that codes to the same preferred term, the subject will be counted only once for that preferred term. Similarly, if a subject has more than one AE within a system organ class category, the subject will be counted only once for that system organ class category.

TEAEs will also be summarized by maximum severity and by strongest relationship to treatment. Serious adverse events (SAEs) will be tabulated and listed in a manner similar to TEAEs. A listing of all AE data will be provided to supplement the tabulated results.

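### EIN, hyperplasia or neoplasia found on biopsy ends a woman's participation but is not an SAE unless it also meets a listed outcome, so it carries no 24-hour report

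*Protocol*

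**What the plan says.** All references are to the last protocol version in the file and to the stage 2 SAP.

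- **SAE definition (Protocol 11.1.2).** An SAE is "An adverse drug experience that results in any of the following outcomes: death, a life-threatening experience, requires or prolongs subject hospitalization", and the list closes with "results in persistent or significant disability/incapacity, or is a congenital anomaly or birth defect". One addition follows: "Cases of liver transaminases that increase above 3 times the upper limit of normal must be reported as SAEs", whether or not a listed outcome is met.
- **Reporting clock (Protocol 11.1.3).** SAEs "must be reported to the Repros Therapeutics Inc. Safety Monitor within 24 hours by Fax or telephone". The section repeats the transaminase addition and names no other finding.
- **Endometrial findings (Protocol 8.3).** A thickness of 18 mm or more leads to a biopsy, and "The endometrial biopsy will be forwarded to a member of the Expert Panel for expedited review". Then: "If EIN or hyperplasia is diagnosed the sponsor will be notified and subject discontinued from the study". A separate bullet says "Subjects with a biopsy that shows clear evidence of neoplasia, as determined by the expert panel, will be discontinued" and makes these women ineligible for further treatment cycles. It mentions no notification.
- **Tables (SAP 6.8.1).** All TEAEs are summarized by treatment group, system organ class and preferred term, and also by maximum severity and strongest relationship. "Serious adverse events (SAEs) will be tabulated and listed in a manner similar to TEAEs". A listing of all AE data is also planned.

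**The concern.** The protocol treats an endometrial diagnosis as grave enough to end participation, yet its safety-reporting section does not mention one. The transaminase override shows that the authors saw that the outcome list could miss a finding relevant to the drug, and they closed the gap for the liver. Nothing equivalent is written for the endometrium, and no general criterion would bring such a finding in.

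At stake is how soon the sponsor's safety function learns of a case and how the case is labelled. Timing matters because other women are still being dosed. Under 8.2.1, women may also go on to as many as two further 16-week active cycles, and those who had placebo move to active drug. A pre-malignant or malignant endometrial diagnosis is information one would want before more women start those cycles.

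**Working it through.** No arithmetic applies: the question is the scope of a definition. The check sets four sections side by side and follows three findings through them, each assumed to occur without a listed outcome such as hospitalization or threat to life.

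| Finding, no listed outcome met | Discontinuation by that finding (8.3) | SAE (11.1.2) | 24-hour report (11.1.3) | SAP output (6.8.1) |
|---|---|---|---|---|
| Transaminase of, say, 3.1 times ULN, with normal bilirubin and INR and no symptoms | Not by that value alone | Yes, by the override | Yes | SAE tables and, if treatment-emergent, TEAE tables |
| EIN or hyperplasia on panel review | Yes | No | No; sponsor notified, no time limit | TEAE tables and AE listing only |
| Neoplasia on panel determination | Yes | No | No; no notification stated in that bullet | TEAE tables and AE listing only |

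The steps behind the table:

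1. **Is the outcome list open or closed?** It names death, threat to life, hospitalization, disability or incapacity, and congenital anomaly, then stops. A diagnosis made on an outpatient biopsy does not in itself meet any of these.
2. **Does the override reach the endometrium?** No. It covers transaminases only, in both places where it appears.
3. **Does 8.3 supply a substitute clock?** Only in part. The expedited step is the pathology review by the Expert Panel. The notification sentence for EIN and hyperplasia gives no deadline and no pointer to 11.1.3. The neoplasia bullet covers discontinuation and eligibility for extension and is silent on notification.
4. **Is the event still recorded?** Yes. A biopsy diagnosis meets the AE definition in 11.1.2, goes on the CRF under 11.1.1, and enters the TEAE summaries and the AE listing under SAP 6.8.1. The SAE tables depend on SAE status, so it is absent from those.
5. **What if a listed outcome is met?** The finding is then already an SAE with a 24-hour report. Section 8.3 foresees bleeding that needs curettage or hysterectomy, and some of those cases may qualify through hospitalization.

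The first row and the other two run in opposite directions. A laboratory value that does not by itself stop treatment under 8.3 is reported within 24 hours, while a diagnosis that does stop treatment has no such report.

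**The case against.** **The events are not lost.** This is correct, and it limits the point. A reader might infer that an endometrial case could disappear from the safety results, or that a zero in the SAE table would understate the risk by a calculable amount. The documents do not support that. The case appears among TEAEs, the AE form records whether the event led to stopping study medication, and no bound on the endometrial risk is planned from the SAE count. A confidence limit attached to a missed case would therefore measure a label and not an unobserved event.

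**Some cases already qualify, and 8.3 has its own route.** Both are true. It would be too strong to say that endometrial findings as a class fall outside SAE reporting, or that the sponsor is never told. What stands is narrower: the notification has no deadline, and for neoplasia it is not stated. Nor does the text support saying that a site would hold a case until a monitoring visit, because no section ties AE reporting to such visits.

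**Liver and endometrium need not be treated alike.** Section 6 cites FDA guidance for classing liver enzyme elevations as SAEs, and nothing visible asks for the same for the endometrium. Which events to designate is partly a design choice, and the protocol does not rank organ risks. However, the override goes beyond the criteria listed in Section 6, where a rise of 3 times ULN counts only with raised bilirubin or with clinical signs or symptoms. The sponsor was therefore willing to designate events on its own judgement. The missing important-medical-event criterion is also a gap whichever organ is considered.

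**Redaction.** Text after 6.5, all of 8.2.5 and a phrase inside the reporting sentence of 11.1.3 are blacked out. The visible SAP ends at 6.8.1. A change log records that a safety board was set up for all Proellex studies, but what it receives is not visible. A separate endometrial rule or table cannot be excluded, so nothing can be said about what that board or any other reviewer of SAEs would see. The SAE definition itself shows no redaction, and 8.3 points to no other rule.

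**Conclusion.** The concern holds in limited form. Followed as written, 8.3, 11.1.2 and 11.1.3 let a biopsy diagnosis of EIN, hyperplasia or neoplasia end participation without being an SAE, unless it also meets a listed outcome. The consequence is the lack of a 24-hour report and of an entry in the SAE tables. The size is the difference between a 24-hour report and either an untimed notification (EIN, hyperplasia) or none stated in the bullet (neoplasia). The recorded data and the TEAE summaries are unaffected.

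This rests on two assumptions: that sites apply the SAE list literally, and that no redacted or unseen section contains a separate endometrial reporting rule.

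**What to change.** Reconcile 8.3, 11.1.2 and 11.1.3:

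- In 11.1.2, add an important-medical-event criterion to the SAE definition.
- Beside the liver override in 11.1.2 and 11.1.3, list panel-confirmed EIN, hyperplasia and neoplasia as events to be reported as SAEs.
- In 8.3, replace the untimed notification with a pointer to the 24-hour report in 11.1.3, and make it cover the neoplasia bullet too.

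The biopsy and discontinuation rules are not touched. The SAP needs no new table, since these events would enter its existing SAE output. If a redacted section already contains such a rule, a cross-reference from 8.3 and 11.1.3 is enough.

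The cost is a few sentences of protocol text, a few more expedited reports and a slightly higher SAE count.

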11.1.3 Serious Adverse Events (SAEs)

The Principal Investigator shall document all SAEs in all subjects after signing informed consent [REDACTED] and they must be reported to the Repros Therapeutics Inc. Safety Monitor within 24 hours by Fax or telephone, even if the SAE does not appear to be drug-related. This report should include all available information at the time of notification. This notification should be followed with submitting a SAE Report Form provided by Repros Therapeutics Inc. All additional follow-up reports must be reported to the Repros Therapeutic Inc. monitor as soon as available.

Cases of liver transaminases that increase above 3 times the upper limit of normal must be reported as SAEs regardless of whether the above defined SAE criteria are met.

12. CONCOMITANT MEDICATIONS

12.1 Prescription Analgesics Permitted During the Study

12.1.1 Treatment of Endometriosis-Related Pain

Subjects should not take any analgesics during the study unless necessary for pain. In the event that a subject needs to use prescription analgesics for endometriosis-related pain, one of the following regimens should be prescribed:

- Hydrocodone/Acetaminophen: 5-10 mg/325 -750 mg, 1-2 tabs every 4-6 hours prn
- Ibuprofen 400 mg, 600 mg or 800 mg every 6 hours prn
- Acetaminophen with Codeine: 1 tab 300/30 mg to 300/60 mg every 4 hours prn
- Oxycodone: 5-15 mg every 4-6 hours prn OR 10 mg (continuous release) every 12 hours prn
- Tramadol: 50-100 mg every 4-6 hours prn up to 400 mg/day
- Ponstel (mefenamic acid) (500 mg initial dose, then 250 mg every 6 hours)
- Hydrocodone/Ibuprofen: 7.5/200 mg, 1-2 tabs every 6-8 hrs prn

Any deviation from this list requires pre-approval by Repros. Note: Over-the-counter medications (e.g. ibuprofen, naproxen) do not qualify as prescription medications for entrance into the study, even if a prescription has been written for the specific medication.

12.1.2 Treatment of Non-Endometriosis-Related Pain

If the subject experiences pain (not related to endometriosis), she should be treated as medically appropriate. The choice of drug will depend on the medical condition. Dosage forms and route of administration should be as per product specifications.

All narcotic, non-narcotic and over-the-counter medication for endometriosis-related pain will be captured in the subjects' daily diary.

All narcotic, non-narcotic and over-the-counter medications for non-endometriosis-related pain will be recorded in the appropriate section of the CRF.

Analgesic medications will not be provided by Repros Therapeutics Inc.

12.2 Prohibited Medications

The following medications are prohibited during the study:

- Testosterone
- Progestin
- Androgen
- Estrogen
- Anabolic steroids
- DHEA
- Other hormonal products
- CYP3A4 inhibitors, e.g. atazanavir, clarithromycin, indinavir, itraconazole, ketoconazole, nefazodone, nelfinavir, ritonavir, saquinavir, telithromycin, omeprazole.
- St. John's Wort
- Spironolactone
- Cimetidine

[figure not shown]
12.3 Other Medications Taken During the Study

Any other prescription or over-the-counter medication taken during the study will be recorded in the appropriate section of the CRF. Subject must be on a stable dosage of approved concomitant medications at least 48 hours prior to drug administration.

13. STATISTICAL METHODS

13.1 Determination of Sample Size

Up to 60 female subjects, 20 per dose arm, meeting the inclusion/exclusion criteria will be randomized in a 1-1-1 fashion. The sample size was powered based on the two-sample t-test that will be used to make pairwise comparisons between treatment groups.

a sample of 18 subjects per group would provide 80% power to detect a statistically significant difference between the treatment groups.

13.2 Statistical and Analytical Plan

A statistical analysis will be conducted once all subjects have completed the placebo-controlled portion of the study, Stage 2. A Statistical Analysis Plan will be developed that outlines in detail all planned analyses. This document will be completed prior to unblinding study data for the placebo-controlled portion of the study.

A separate analysis and reporting will occur once all subjects have completed all study treatment. A separate Statistical Analysis Plan will describe these analyses. This summary will focus on the results noted in Stage 3 of the study.

13.2.1 Demographics and Subject Characteristics

For all subjects included in this study, subject accountability, baseline demographic and medical history data will be summarized for each treatment group. Summaries for quantitative variables include the sample size, mean, median, standard deviation, minimum, and maximum. Summaries for categorical variables include the number and percent of patients for each outcome. No statistical testing will be performed to compare these factors between treatment groups.

13.2.2 Efficacy Analyses

An analysis will be conducted once Stage 2, the first cycle of treatment, has been completed. A later analysis will focus on the data collected from the active treatment stage of the study, Stage 3.

Efficacy analyses of the first cycle of treatment will be conducted in the Intent-to-Treat population, which will consist of all subjects who are randomized and who receive study drug. Subjects with missing post-baseline data will have a value of “no change” imputed for analysis.

13.2.2.1 Prescription Analgesic Usage

The change and percent change in daily average use of prescription analgesics comparing the baseline menstrual cycle (28 days) to the 28 days leading up to the last day of dosing in Cycle 1 (Week 18) will be summarized for each treatment group. For each subject, the total number of pills or tablets of prescription analgesics during each 28 day menstrual cycle will be calculated, and the daily average use of prescription analgesics will be determined by dividing the total number of pills/tablets of prescription analgesics taken during the 28 day nominal period by 28. The percent change from baseline in the prescription analgesic usage will be determined by subtracting the baseline prescription analgesic usage from the prescription analgesic usage during the last nominal 28 day menstrual cycle, dividing by the baseline prescription analgesic usage, and multiplying by 100%.

An overall comparison among the 3 treatment groups will be performed using a one-way Analysis of Covariance, including the baseline prescription analgesic usage and treatment group in the model. Pairwise comparisons of the treatment groups will be made using a two-sample t-test. While the primary assessment will be based on Visit 12 (after 18 weeks of treatment) summaries will also be prepared for each of the other visits. If data are missing, a last observation carried forward procedure will be used, including the baseline, if necessary.

Changes in prescription analgesic use during the active treatment stage of the study (Stage 3) will also be summarized.

